9.14. System Modification

System modifications made to the DBS System will be completed according to the center's standard procedures. If the system modification occurs prior to randomization, the subject should be exited, prior to receiving the system modification if possible, and considered for re-enrollment as applicable. If the system modification occurs after randomization, the investigator should assess if the subject should be exited from the study or proceed to the long term follow up phase on aDBS. The subject will not complete or repeat the aDBS evaluation period(s). If the subject proceeds to the long term follow up phase, aDBS will be programmed after (s)he is healed and stable on cDBS. aDBS can be programmed by either performing the full aDBS setup or by using the subject's prior aDBS parameters and assessing for acceptability. Any visits for aDBS setup due to a system modification will be recorded as unscheduled visits. Once aDBS is set up, the subject will enter the long-term follow-up. If aDBS cannot be acceptably set up, the subject will be exited from the study following the process in Section 9.19.

Data collection:

- Device information (if applicable)
- Concomitant medications
- Programming session upload to Medtronic via CDU, with BrainSense data included in the JSON session data report (if INS is being modified)
- Adverse Event and Device deficiency assessment

9.15. Assessment of Efficacy and Device Performance

9.15.1. Parkinson's Disease (PD) Home Diary

The Parkinson's Disease Home Diary (Copyright © The University of South Florida, 2000. All rights reserved) is a standard home diary to assess functional status in patients with PD. In 30-minute intervals, patients record whether they were in the "On" condition, with or without dyskinesia, "Off" condition, or asleep.^a In the On condition with dyskinesia, patients record whether they were On with troublesome or non-troublesome dyskinesia. For the purposes of the PD home diary, at least 3 consecutive days means at least 3 consecutive 24-hour periods.

^a Hauser, et al. "A home diary to assess functional status in patients with Parkinson's disease with motor fluctuations and dyskinesia." Clinical Neuropharmacology. 2000 Mar-Apr;23(2):75-81.

Medtronic Business Restricted

9.15.2. Total Electrical Energy Delivered (TEED)

TEED is defined as the total energy delivered by an electrical system through the DBS leads over an arbitrary period of time. TEED is determined by the stimulation parameters (e.g., pulse width, frequency, amplitude) and the measured impedance.

The calculation of TEED when using constant voltage is:

$$\text{TEED} = (\text{Voltage}^2 * \text{Frequency} * \text{Pulse width}) / \text{Impedance}^b$$

The calculation of TEED when using constant current is:

$$\text{TEED} = \text{Current}^2 * \text{Frequency} * \text{Pulse width} * \text{Impedance}$$

9.15.3. Wearable Data

Wearable data will be collected via the PKG Watch as a continuous measure of bradykinesia score (BKS), dyskinesia score (DKS) and the % of wear time with Tremor. A Fluctuation and Dyskinesia score (FDS) will also be derived from the wearable data.

9.15.4. European Quality of Life – 5 Dimensions (EQ-5D-5L)

The European Quality of Life – 5 Dimensions, version 5L (EQ-5D-5L), is a standardized measure of health status developed by the EuroQol Group and a widely used validated tool to determine health-related quality of life.^c The EQ-5D descriptive system consists of 5 dimensions: mobility, self-care, usual activities, pain/discomfort, and anxiety/depression. Each dimension has 5 levels of severity: no problems, slight problems, moderate problems, severe problems, extreme problems. The subject will be asked to indicate his/her health state by selecting the most appropriate statement in each of the 5 dimensions. This decision results in a 1-digit number expressing the level selected for that dimension. The digits for 5 dimensions can be combined into a 5-digit number describing the respondent's health state. It should be noted that the numerals 1-5 have no arithmetic properties and should not be used as a cardinal score. In a second step, the responses to the five EQ-5D dimensions (i.e. an EQ-5D health state or profile) will be converted into a single number called an index value using the United Kingdom value

^b Koss AM, et al. "Calculating Total Electrical Energy Delivered by Deep Brain Stimulation Systems." *Annals of Neurology*. Vol 58. No 1. July 2005. P. 168-169.

^c The EuroQol Research Foundation. "EQ-5D-5L User Guide: Basic information on how to use the EQ-5D-5L instrument." https://euroqol.org/wp-content/uploads/2016/09/EQ-5D-5L_UserGuide_2015.pdf

Medtronic Business Restricted

set. The index value reflects how good or bad the health state is according to the preferences of the general population of a country/region.

This assessment may be completed either in person, or over the telephone a maximum of 7 days prior to the study visit.

9.15.5. Parkinson's Disease Questionnaire (PDQ-39)

The Parkinson's Disease Questionnaire is a self-completion Patient Reported Outcome (PRO) designed to address aspects of functioning and well-being for those affected by Parkinson's disease.^d There are 39 questions in the long form Parkinson's Disease Questionnaire, with 8 discrete scales:

- mobility (10 items)
- activities of daily living (6 items)
- emotional well-being (6 items)
- stigma (4 items)
- social support (3 items)
- cognitions (4 items)
- communication (3 items)
- bodily discomfort (3 items)

Patients are asked to think about their health and general well-being and to consider how often in the last month they have experienced certain events (e.g. difficulty walking 100 yards). Patients are asked to indicate the frequency of each event by selecting one of 5 options (Likert Scale): never/occasionally/sometimes/often/always or cannot do at all.

This assessment may be completed either in person, or a copy may be sent to the subject to be completed a maximum of 7 days prior to the study visit.

9.15.6. Movement Disorders Society Unified Parkinson's Disease Rating Scale (MDS-UPDRS)

The MDS-UPDRS is a MDS-sponsored revision of the UPDRS clinical rating scale for Parkinson's disease. It has been the most widely used scale to assess impairment and disability in PD. The MDS-UPDRS is a comprehensive 50 question assessment of both motor and non-motor PD symptoms. The assessment has four parts: Part I (non-motor experiences of daily living), Part II (motor experiences of daily living),

^d Oxford University Innovation. "Parkinson's Disease Questionnaire (PDQ-39 and PDQ-8)." <https://innovation.ox.ac.uk/outcome-measures/parkinsons-disease-questionnaire-pdq-39-pdq-8/>

Medtronic Business Restricted

Part III (motor examination) and Part IV (motor complications).^e Parts 1A, III and IV are assessed by the trained rater and Parts IB and III are a self-administered patient questionnaire that is completed with or without the aid of the caregiver.

Each question is scored from 0 to 4 reflecting the subject's usual level of function; Normal, Slight, Mild, Moderate and Severe. Each part (I-IV) can be reported as sub-scores, or all parts can be reported as an overall score.

This assessment must be completed in person whenever possible. In the event the assessment cannot be completed in person, Parts IA, IB, II and IV may be administered via telephone/telehealth a maximum of 7 days prior to the study visit, and a protocol deviation recorded.

9.15.7. Parkinson's Disease Sleep Scale 2 (PDSS-2)

The PDSS-2 assesses a wide spectrum of disease-specific sleep problems and is administered as a patient self-rating scale.

The PDSS-2 consists of 15 questions about various sleep and nocturnal disturbances which are to be rated by the patients using one of five categories, from 0 (never) to 4 (very frequent). PDSS-2 total score ranges from 0 (no disturbance) to 60 (maximum nocturnal disturbance).^f

This assessment must be completed in person whenever possible. In the event the assessment cannot be completed in person, the assessment may be administered via telephone a maximum of 7 days prior to the study visit, and a protocol deviation recorded.

9.15.8. Voice Handicap Index (VHI)

The VHI has been designed to evaluate the quality-of-life specific to dysphonia. It was developed and validated with patients with a wide range of disorders, including neurological disorders and quantifies the patients' perceptions of the handicap they experience in everyday life due to speech disorders.

The 30-item self-administered questionnaire consists of a 10-item functional subscale, a 10-item emotional subscale, and a 10-item physical subscale. Patients are asked to read each item and circle one of five response comprising an equal-appearing five-point scale. The scale has the words "never" and "always" anchoring each end and the words "almost never", "sometimes", and "almost always"

^e Movement Disorder Society. "MDS-UPDRS." https://www.movementdisorders.org/MDS-Files1/PDFs/Rating-Scales/MDS-UPDRS_English_FINAL_Updated_June2019.pdf

^f Trenkwalder C, et al. "Parkinson's Disease Sleep Scale – Validation of the Revised Version PDSS-2." Movement Disorders. Vol. 26. No. 4. March 2011. P. 644-652.

Medtronic Business Restricted

appearing in between. An “always” response was scored 4 points, a “never” response was scored 0 points, and the remaining options were scored between 1 and 3 points. ⁸

This assessment may be completed either in person, or a copy may be sent to the subject to be completed a maximum of 7 days prior to the study visit.

9.15.9. Patient Preference

Patient preference for aDBS vs. cDBS and Single vs. Dual Threshold aDBS modes (if both were evaluated) will be assessed by a Medtronic-developed questionnaire.

This assessment may be completed either in person, or a copy may be sent to the subject to be completed a maximum of 7 days prior to the study visit.

9.15.10. Patient Satisfaction

Patient satisfaction with aDBS as assessed by a Medtronic-developed questionnaire.

This assessment may be completed either in person, or a copy may be sent to the subject to be completed a maximum of 7 days prior to the study visit.

9.15.11. aDBS Global Impression of Change

Acceptability of each aDBS mode is be assessed by a Medtronic-developed aDBS Global Impression of Change. Efficacy and side effects are assessed on a scale from 1 to 21. Lower scores represent better efficacy and fewer side effects. A score of 8 or less indicates the aDBS mode is acceptable.

9.16. Assessment of Safety

Subjects will be assessed for all potential Adverse Events and device deficiencies, as applicable, at each study visit from the time the study informed consent form is signed until discontinuation from the study. Safety data collected for this study will include all device deficiencies, and all reportable AEs. Refer to [Section 11: Adverse Events and Device Deficiencies](#).

⁸ Jacobson B, et al. “The Voice Handicap Index (VHI): Development and Validation.” American Journal of Speech-Language Pathology. Vol 6. No 3. August 1997. P. 66-70.

Medtronic Business Restricted

9.17. Recording Data

The investigator must ensure accuracy, completeness and timeliness of the data reported in the case report forms (CRFs) and in all other required reports. Source documentation is defined as the first time data appear, and may include original documents, data, and records (e.g., hospital records, clinical and office charts, procedure reports, laboratory notes, memoranda, subjects' diaries or evaluation checklists, pharmacy dispensing records, recorded data from automated instruments, copies or transcriptions certified after verification as being accurate copies, microfiches, photographic negatives, microfilm or magnetic media, X-rays, subject files, device data and records kept at the pharmacy, at the laboratories and at medico-technical departments involved in the study).

In general, eCRFs (or paper copies) may not serve as source documents. Subject questionnaires (e.g. PD Home Diary, MDS-UPDRS, VHI, PDQ-39, PDSS-2) and physician assessments (e.g. C-SSRS, GIC, MDS-UPDRS) may be collected on paper forms provided by the sponsor to be entered into the RDC system by the center personnel. If used, the paper forms of the questionnaires will be retained at the center as original source documentation. Source documentation for data elements not routinely captured in medical records may vary from study site to study site; the study site may use source document worksheets if identified as source documents. Data reported on the CRFs, which are derived from source documents, must be consistent with the source documents and discrepancies need to be justified with documented rationale, and approved by the principal investigator or delegate. The investigator must ensure the availability of source documents from which the information on the eCRFs was derived. Where printouts of electronic medical records are provided as source documents, or where copies of source documents are retained as source documents, those should be certified. Certification must contain (1) the signature of the individual making the copy, (2) the date the copy was made and (3) a statement attesting to the accuracy and completeness of the copy.

The source documents must be made available for monitoring or auditing by Medtronic's representative or representatives of the competent authorities and other applicable regulatory agencies.

The study will use the Oracle Clinical (OC) RDC system which allows the study centers to enter study data into the sponsor's database over a secured internet connection. The system controls user access, ensures data integrity, and maintains an audit trail on entries, changes or corrections in CRFs. The principal investigator will ensure that only appropriately delegated study personnel are given access to the RDC system; user IDs and passwords may not be shared.

Programming session files, with BrainSense data included in the JSON session data report, will be collected for the study and uploaded via CDU to the NPU (Neuro Programmer Upload) server and study database.

Medtronic Business Restricted

9.18. Deviation Handling

A study deviation is an event within a study that did not occur according to the clinical investigation plan, CTA, investigator agreement, IRB/EC policies or applicable standards, laws and regulations.

The investigator may not deviate from the CIP unless the deviation is necessary in an emergency situation to protect the rights, safety and wellbeing of the subject. or due to an unforeseen circumstance that is beyond the investigator's control (eg, subject failure to attend a scheduled follow-up visit, inadvertent errors, equipment failure). All deviations must be documented in the study database whether an inadvertent occurrence or taken to protect the subject in an emergency. Multiple deviations of the same type at the same visit may be reported on one case report form.

In the event the deviation involves a failure to obtain a subject's consent, or is made to protect the life or physical well-being of a subject in an emergency, the deviation must be reported to the IRB/EC as well as Medtronic within five (5) working days. Reporting of all other study deviations should comply with IRB/EC policies and/or local laws and must be reported to Medtronic as soon as possible upon the study site becoming aware of the deviation. Reporting of deviations must comply with IRB/EC policies, local laws, and/or RA requirements. Refer to [Section 15.8.1](#) for geography-specific deviation reporting requirements and timeframes for reporting to Medtronic and/or RAs.

Deviations include, but are not limited to, the following:

- Failure to obtain subject informed consent prior to beginning study activities
- Subject does not meet general inclusion/exclusion criteria after the enrollment visit
- Failure to report AEs or Device Deficiencies per [Table 9: Safety Reporting Requirements](#)
- Failure to collect CIP-required assessments
- Subject missed visit or visit outside of window
- Subject unblinding
- Programming adjustments during the 14 days prior to each aDBS Evaluation Visit
- For subjects with the SenSight system enrolled in the Primary Cohort: change of programming from ring mode to directional stimulation before the end of the aDBS Evaluation Phase
- For subjects enrolled in the Directional Stimulation Cohort: change of programming from directional stimulation to ring mode before the end of the aDBS Evaluation Phase

Deviations will be reviewed by Medtronic on an ongoing basis. Medtronic will assess the significance of all deviations for the study and evaluate the need for any corrective and/or preventative actions (e.g. amend the CIP, conduct additional training, terminate the study). Repetitive or serious investigator compliance issues may suggest a need to implement a corrective action plan with the investigator and study center. If needed, subject enrollment may be suspended until the compliance issues are resolved. If compliance issues are left unresolved, the investigator's participation in the study may be terminated.

Medtronic will provide study site-specific reports to investigators summarizing information on deviations that occurred at the investigational study site on a periodic basis.

Medtronic Business Restricted

During the aDBS Evaluation Phase, every effort should be made to keep the subjects in the study, with applicable protocol deviations reported as necessary.

9.19. Subject Exit, Withdrawal or Discontinuation

Subjects will discontinue the study following completion of all study visits.

Prior to early discontinuation, or after the completion of the final study visit if aDBS is not commercially available, subjects will return to the study center to have aDBS turned off and be programmed back to standard cDBS Therapy. This is done by interrogating the subject's INS with a commercially available Clinician Programmer System. The subject will return the investigational Patient Programmer System to the study center and the investigator will re-pair the subject's INS with a commercially available Patient Programmer System. A final device interrogation will be obtained to confirm that aDBS has been turned off. The programming session, with BrainSense data included in the JSON session data report, will be uploaded to Medtronic via CDU. BrainSense and passive sensing functionality will be on or off at the discretion of the clinician. Once aDBS is no longer active, the subject's INS is no longer considered Investigational, and subjects will be discontinued and followed according to the study center's standard procedures.

If a subject discontinues from the study prior to normal completion, the eCRFs for visits that have occurred up to the point of withdrawal as well as the study exit eCRF must be completed.

After study discontinuation, the updates for ongoing, and for any new events (eg, AEs or device deficiencies), will be reported through Neuromodulation Customer Quality as required by regulation.

9.19.1. Study Exit

A study exit eCRF is required for all subjects. Subjects are urged to remain in the study as long as possible but may be exited from the study for any of the following situations:

- Study completed (visit #6)
- Subject lost to follow-up
- Subject death
- Subject's DBS Therapy System permanently explanted (i.e., neurostimulator, lead, extension)
- Subject did not meet inclusion/exclusion criteria (prior to randomization)
- Subject did not provide consent or data use protection authorization
- Subject chooses to withdraw (e.g., consent withdrawal, relocation to another geographic location)
- Investigator deems withdrawal necessary (e.g., medically justified, inclusion/exclusion criteria not met, failure of subject to maintain adequate study compliance)
- Neither aDBS mode is acceptable

Medtronic Business Restricted

The Investigator will attempt to collect the following information prior to the subject's early discontinuation from the study:

- Adverse event and device deficiency assessment
- Programming session report, with BrainSense data included in the JSON session data report upload to Medtronic via CDU (after aDBS has been turned off)
- A brief description of why the subject discontinued (if applicable)
- Patient satisfaction questionnaire (if early discontinued after the aDBS Evaluation Phase)

9.19.2. Study Completed

At the completion of Visit 6, subjects may exit from the study. Both the CRFs for Visit 6 and a Study Exit CRF need to be completed. If aDBS is not commercially approved at the time the subject completes all study visits, the subject may choose to continue participation in the study until aDBS is commercially approved or closure of the study, whichever comes sooner.

9.19.3. Lost to Follow-up

A subject is considered to be lost to follow-up if at least two attempts to contact the subject are unsuccessful. The method of attempt (e.g., one letter and one phone record, or two letters) must be documented in the subject's medical record. In addition, regulation set forth by the governing IRB/EC must be followed.

When subjects are lost to follow-up the investigator will make efforts to confirm the vital status of the subject, as described in the informed consent.

9.19.4. Subject Chooses to Exit (i.e. Revokes Consent)

A subject can withdraw from the study at any time. If the subject wishes to exit from the study (i.e., the subject revokes consent), the study site is required to document the reason for exit on the Exit CRF. In addition, study sites shall follow the regulations set forth by the governing IRB/EC. Permission may be requested to follow up with the subject outside of the study due to withdrawal based on problems related to the investigational feature safety or performance.

If possible, the following data should be collected prior to subject withdrawal:

- Adverse event and device deficiency assessment
- Final device interrogation and data upload via CDU (after aDBS has been turned off)
 - Export JSON Session Data
- A brief description of why the subject discontinued (if applicable)

Medtronic Business Restricted

9.19.5. Investigator Withdraws Subject

No subjects should be withdrawn by investigators unless compelling medical justification is present. It is recommended investigators discuss any withdrawals with the study team prior to withdrawing subjects. If the subject was randomized, it is preferred to keep the subject in the study and perform study procedures/collect data to the extent possible. If an investigator withdrawal is necessary, the following data should be collected prior to subject withdrawal if possible:

- Adverse event and device deficiency assessment
- Final programming session upload to Medtronic via CDU, with BrainSense data included in the JSON session data report (after aDBS has been turned off)
- A brief description of why the subject was withdrawn by the investigator

9.19.6. Conditional Disengagement

After a subject is enrolled/randomized every effort should be made to keep the subject in the study. However, it is recognized that there are circumstances where limited data may be collected, or study exit will need to occur. In these cases we will consider either modified data collection requirements where subjects may conditionally disengage in study procedures but data from the subject can still be collected because the subject has not revoked consent, or exit when study participation is completely ended. In randomized subjects, modified data collection is always preferred over exit.

Subjects may be conditionally disengaged from study procedures for any of the following reasons:

- Subject chooses to disengage (e.g., follow-up schedule cannot be adhered to, study burden too large, relocation to another geographic location but telephone follow-up still acceptable)
- Investigator deems conditional disengagement necessary (e.g. medically justified)

If the subject wishes to disengage from the study, or the investigator deems it necessary, the study site is required to document the reason. Prior approval from the study team is required and a Limited Data Collection CRF needs to be completed. Data collection requirements no longer apply, but study sites are encouraged to collect as much data as possible on the regular CRFs.

10. Risks and Benefits

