11.4. Definitions/Classifications

This study will be following ISO14155:2020 and will collect all Adverse Events and Device Deficiencies from the time of enrollment through study exit/discontinuation. It is the responsibility of the Investigator to identify the occurrence of all adverse events and device deficiencies and to ensure the required information is accurately documented in the medical records and reported to Medtronic. Where the definition indicates "device", it refers to any device used in the study. This might be the device under investigation, or any market released component of the system, and includes but is not restricted to the components listed in [Table 1: Medtronic DBS System Components](#) and the PKG Watch.

Table 7: Adverse Event and Device Deficiency Definitions

General	
Adverse Event (AE)	Untoward medical occurrence, unintended disease or injury, or untoward clinical signs (including abnormal laboratory findings) in subjects, users or other persons, whether or not related to the investigational medical device and whether anticipated or unanticipated. Note 1: This definition includes events related to the investigational medical device or the comparator. Note 2: This definition includes events related to the procedures involved. Note 3: For users or other persons, this definition is restricted to events related to the use of investigational medical devices or comparators. (ISO 14155:2020, 3.2)
Adverse Device Effect (ADE)	AE related to the use of an investigational medical device. Note 1: This definition includes AEs resulting from insufficient or inadequate instructions for use, deployment, implantation, installation, or operation, or any malfunction of the investigational medical device. Note 2: This definition includes any event resulting from use error or from intentional misuse of the investigational medical device.

Medtronic Business Restricted

	
NOTE 3: this includes 'comparator' if the comparator is a medical device (ISO 14155:2020, 3.1)

Device Deficiency	
Inadequacy of a medical device with respect to its identity, quality, durability, reliability, usability, safety or performance.
 
Note 1: DD include malfunctions, use errors and inadequacy in the information supplied by the manufacturer including labeling.
 
Note 2: This definition includes device deficiencies related to the investigational medical device or the comparator. (ISO 14155:2020, 3.19)

Relatedness	

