Serious adverse events, adverse events, and device deficiencies that occur from the time of enrollment through study exit/discontinuation will be summarized for all enrolled subjects. Analyses will be conducted on the AT analysis set for subjects in the Primary Cohort and on the DSAT for subjects in the Directional Stimulation Cohort. The denominator will include the appropriate number of subjects for each respective phase, period, and cohort. Events will be summarized by number of events, number of subjects who experienced the event, and percentage of subjects who experienced the event.

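### CIP 9.19.6 waives data collection for conditionally disengaged subjects without keeping adverse-event and device-deficiency reporting, which contradicts Section 11

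*Protocol*

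**What the plan says.** CIP 9.19.6 separates disengagement from exit. A disengaged subject remains in the study, and "data from the subject can still be collected because the subject has not revoked consent". The stated preference is clear: "In randomized subjects, modified data collection is always preferred over exit". On what is then collected, the section speaks first of "modified data collection requirements where subjects may conditionally disengage in study procedures", and later states flatly: "Data collection requirements no longer apply, but study sites are encouraged to collect as much data as possible on the regular CRFs". Two formal steps remain: "Prior approval from the study team is required and a Limited Data Collection CRF needs to be completed". The content and timing of that CRF are not described.

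Section 11.4 sets a different rule. The study "will collect all Adverse Events and Device Deficiencies from the time of enrollment through study exit/discontinuation". Sections 11.1 and 11.2 likewise run AE and device-deficiency collection for the whole study.

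On the device, Section 9.19 has a turn-off step. It applies ahead of early discontinuation, or once the last visit is done where aDBS is not yet on the market. The step reads: "subjects will return to the study center to have aDBS turned off and be programmed back to standard cDBS Therapy". Section 9.19.6 does not mention aDBS status.

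**The concern.** A disengaged subject has an implanted device and may still be receiving investigational stimulation. The CIP gives the site two incompatible instructions about that subject's safety data and does not say which prevails. If the waiver is taken at its word, AEs and device deficiencies in a subject who is still consented and enrolled could go uncollected. Exit triggers an attempt at a final AE and device-deficiency assessment and a programming upload (9.19.1). Disengagement triggers no comparable step. The safety summaries, and the protection of the subjects themselves, rely on collection continuing until exit.

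**Working it through.** **1. What the waiver covers.** Section 9.2 says that data collection requirements are the ones summarized in Table 3. That table has rows for AEs, device deficiencies and protocol deviations, each to be recorded whenever they occur. Section 9.19.6 uses the same term and carves nothing out. Read with the CIP's own term, the waiver reaches the AE and device-deficiency rows.

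**2. What the other sections require.**

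- 9.16: AEs and device deficiencies are assessed at each visit from consent until discontinuation.
- 9.18: failing to report AEs or device deficiencies per Table 9 is a listed deviation.
- 11.1 and 11.2: both are collected throughout the study.
- 11.3: AE follow-up ends at resolution, no further planned action, death, exit or study closure. Disengagement is not on the list.
- 11.4: collection runs from enrollment to exit or discontinuation.
- Table 9: events are reported to the sponsor, with several of the time limits counted from the site's awareness.

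None of these mentions disengagement, and 9.19.6 does not refer to Section 11. A disengaged subject has not exited, so both rules apply and they conflict.

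**3. Whether Section 11 alone closes the gap.** Only in part. Reporting that starts from awareness needs a route to awareness. The active route in 9.16 is the study visit, and a subject disengaged from procedures may have none. Section 9.19.6 mentions telephone follow-up only as an example within one reason for disengaging. It requires no contact.

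**4. Scale.** The documents do not give the number of disengaged subjects, so what follows is a range under assumption, not an estimate.

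The plan's own safety figure (CIP 13.2.4, SAP Section 6) is at least 95% probability that an event with a true rate of 10% is reported at least once among 30 subjects. It reproduces: 1 − 0.9^30 = 0.9576. The smallest number that reaches 95% is 29 (0.9529); 28 gives 0.9477.

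Assume that k disengaged subjects contribute no AE data at all, so that n − k remain:

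| Starting n | Largest k still at or above 95% | First k below 95% |
|---|---|---|
| 30 | 1 (0.9529) | 2 (0.9477) |
| 36 | 7 (29 remain, 0.9529) | 8 (0.9477) |
| 40 | 11 (0.9529) | 12 (0.9477) |

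If those subjects stay in the denominator, the expected observed rate is 0.10 × (n − k)/n. For 2 of 30 it is 0.10 × 28/30 = 9.3%. For 4 of 36 it is 0.10 × 32/36 = 8.9%. For 4 of 40 it is 0.10 × 36/40 = 9.0%. If half of the events in the 4 of 40 were still captured, it would be (0.10 × 36 + 0.05 × 4)/40 = 9.5%.

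**5. Longest possible exposure.** From Table 4, Day 0 to Visit 6 with two modes is 30+30+45+45+76+76 = 302 days to 45+45+60+60+104+104 = 418 days. With one mode it is 302−30 = 272 to 418−45 = 373 days. This is a ceiling. It would be reached only by a subject who disengaged immediately after Day 0, remained on aDBS throughout, and had Section 11 disregarded.

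**The case against.** The strongest reply is that Section 11 governs safety reporting and exempts nobody, so the waiver can be read as covering scheduled procedures only. The same section speaks of modified rather than abolished requirements, and it demands a documented reason, study-team approval and a dedicated CRF. That CRF is not in the documents, so nobody can say that it omits AEs or aDBS status. This reading is available, and it stands against any claim that AE reporting has become optional. It does not remove the conflict. The waiver is unqualified, the CIP's own term includes AEs, and nothing says that Section 11 prevails.

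A reader might infer more than the documents support:

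- **That events are under-counted.** No count of disengaged subjects is given, and the detection figure is robust from 40 subjects: 11 could contribute nothing and it would remain above 95%.
- **That the subjects who disengage are those doing badly on aDBS, biasing rates downward.** The subject-side examples are schedule, burden and relocation. Medical justification is one investigator-side example and names no cause. Subjects whose chosen mode after the Evaluation Phase is cDBS are exited (9.10.2).
- **That 9 to 14 months of AEs go uncollected.** Those spans stack three worst-case assumptions. Most of that time is long-term follow-up, whereas the stimulation-related AE comparison covers only the Baseline and Evaluation Phases, with 30 to 45 days per mode.
- **That exiting subjects are clearly better covered.** Their final assessments are also best-effort, and later events leave study reporting. Disengagement postpones the exit steps; it does not remove them.
- **That the SAP denominator needs a new rule.** SAP 7.10 says only: "The denominator will include the appropriate number of subjects for each respective phase, period, and cohort". Once AE collection is confirmed until exit, disengaged subjects belong in it like any others.

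**Conclusion.** The concern holds as an internal contradiction that should be corrected. Section 9.19.6, read with 9.2 and Table 3, waives AE and device-deficiency collection for subjects still in the study. Sections 9.16, 9.18 and 11.1 to 11.4 and Table 9 require it until exit. The section is also silent on recording aDBS status, while the turn-off step in 9.19 is tied to discontinuation or the final visit.

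This is more than a missing cross-reference, because a site could follow the sentence as written in good faith and visit-based ascertainment may stop. The consequence is a possible loss of safety events, not a demonstrated one. Its size depends on two unknowns: how many subjects disengage, and how sites read the sentence. Safety analyses are descriptive with no success criterion, so no trial conclusion turns on this point.

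**What to change.** Amend the sentence in CIP 9.19.6 along these lines:

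> Scheduled efficacy and questionnaire requirements no longer apply. Collection and reporting of AEs, serious AEs, deaths and device deficiencies under Section 11 and Table 9 continue until study exit; telephone contact is acceptable where visits stop. The Limited Data Collection CRF records whether aDBS is on or off.

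Reconcile 9.19.6 with 9.19 on aDBS status. The request is for the status to be recorded and the passages to agree; no clinical rule is proposed. No change to SAP 7.10 is needed.

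The cost is a short CIP amendment with its usual approvals, a field on an existing CRF, and brief telephone contacts for however many subjects disengage, probably few. Section 9.19.6 already contemplates telephone follow-up.
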